8.2 Endpoints

8.2.1 Primary Endpoint(s)

8.2.1.1 Primary Efficacy Endpoint

A subject will meet the primary endpoint if a paced or sensed ventricular beat is within 300 ms following an ECG confirmed P-wave for at least 70% of the ECG confirmed P-waves. The primary endpoint will be evaluated during the MARVEL 2 setup phase (VDI pacing which is effectively VVI pacing) and during the 20-minute resting period in which the MARVEL 2 features are enabled.

Rationale for Endpoint

Rationale for 300 ms Synchronous Beat Definition

A paced or sensed R-wave within 300 ms of following an ECG confirmed P-wave that occurs during normal sinus function indicates a level of atrioventricular synchrony that is clinically acceptable. Specifically, currently available dual chamber Medtronic pacing systems utilize the Search AV+[®] algorithm that allows for maximum nominal AV intervals to be lengthened to 290 ms (for intrinsic sensed events) and 320 ms (for paced events) to limit unnecessary ventricular pacing. This feature has been shown to minimize ventricular pacing and reduce atrial fibrillation in patients with sinus node disease.⁷ Therefore, a pace or detection of a sensed R-wave following within 300 ms of an ECG confirmed P-wave would indicate an acceptable level of atrioventricular synchrony.

Additionally, only P-waves identified on surface ECG that occur during normal sinus node function will be considered for the endpoint. Therefore, P-waves occurring during atrial arrhythmias are not included in the endpoint definition. This criterion was selected so that atrial beats that should not or could not be tracked by the algorithm with a paced or sensed ventricular beat are not included in the endpoint determination. Note that the 300 ms P-V interval required to consider a beat synchronous is identical to what was used for the MARVEL study.

Rationale for 70% AV Synchrony Requirement

There is no recognized consensus on a clinically relevant level of atrioventricular synchrony for subjects with AV block and without AF who require pacing. Importantly, the largest randomized trial (UKPACE) comparing VVI and DDD pacing in patients with normal sinus function and AV block did not identify a difference in pacing modes with respect major clinical outcomes including all-cause mortality, atrial fibrillation, or heart failure.⁸ However, as observed in the MARVEL study, increasing the level of synchrony in this population can increase cardiac stroke volume.⁶

[figure not shown]

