17.5.3 Sample Size

A sample size of at least 35 subjects with normal sinus node function and persistent 3rd degree AV block and a sufficient number of evaluable cardiac cycles during the vector setup and 20-minute resting period will provide greater than 90% power to reject the null hypothesis based on the following assumptions:

[figure not shown]
1. Two-sided type I error rate = 0.05
2. Single analysis after all enrolled subjects have had an opportunity to complete the MARVEL 2 study procedures and have had their Holter data evaluated
3. Each subject will have at least 500 evaluable beats* during the auto-setup phase (VVI pacing) period and during VDD pacing during the 20-minute resting period
4. The proportion of subjects meeting the primary efficacy endpoint in one pacing mode, but not the other (i.e. proportion of discordant pairs) will exceed 50%
5. At least 90% of discordant subjects will favor the MARVEL 2 features

**Note: An evaluable beat is defined as an observable P-wave on the Holter ECG followed by at least 300 ms of drop-out free Holter telemetry data or a Micra ventricular event marker.*

Justification of Sample Size Assumptions

Figure 5 displays the AV synchronous pacing percentage observed in the MARVEL study by predominant rhythm. The average AV synchronous pacing percentage among the 33 subjects with a predominant rhythm of high-grade AV block was 80.0% during MARVEL adaptive mode (VDD pacing) compared to 37.5% during VVI pacing ($P < 0.001$). Among the 33 subjects with a predominant rhythm of high-grade AV block, 72.7% of subjects (24 of 33) had an AV synchronous pacing rate exceeding 70% while in MARVEL adaptive mode compared to 6.1% (2 of 33) during MARVEL monitor mode (VVI pacing).

Figure 5: AV Synchronous Pacing Percentage Observed in the MARVEL Study by Predominant Rhythm

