Similar to the original MARVEL study, Holter files will be processed and reviewed by Medtronic personnel experienced in the review of Holter recordings using Holter and MATLAB utilities. A human overread will also be used to truth each P-wave. Device and MARVEL 2 markers will not be used by the MATLAB scripts or human overread to identify P-waves. Finally, a MATLAB script will collate the identified P-waves, times corresponding to distinct study procedures, and MARVEL 2 markers in a .csv format file. This .csv file will indicate the time after each P-wave a ventricular pace or intrinsic sensed R-wave occurred. Comparison of this P-R interval to 300 ms will determine whether a beat was synchronous. If at least 70% of beats are considered synchronous during the VVI or MARVEL 2 adaptive pacing mode during resting, then the subject will be considered to have met the primary efficacy endpoint during the VVI or MARVEL 2 adaptive pacing mode during rest respectively. McNemar's test for paired proportions will be used to test the primary efficacy objective hypothesis.

The following pre-specified subgroups will be evaluated: sex, geography (US versus outside of US), and participation in the MARVEL study (yes versus no). A repeated measures logistic regression model utilizing generalized estimating equations will be used to evaluate the homogeneity of the MARVEL 2 adaptive pacing mode effect on the primary efficacy endpoint by subgroup. For this model, the response will be the primary endpoint status (1=met primary endpoint, 0=did not meet) and the independent variables will be the pacing mode (VVI pacing or MARVEL 2 adaptive mode), subgroup status, and a subgroup status by pacing mode interaction.

Additionally, the proportion of subjects meeting the primary efficacy endpoint will be summarized and compared between VVI pacing and MARVEL 2 adaptive pacing using the methods described above in the following subsets of subjects with normal sinus node function and persistent 3rd degree AV block:

1. Those subjects exhibiting low PVC burden
2. Those subjects exhibiting low PVC burden with a mitral valve doppler echo E/A ratio of 1.5 or less

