7.5.3.4 Analysis Methods

For each subject, the VVI pacing control period will occur shortly following investigational software download during the approximately 20-minute algorithm auto-setup phase where the MARVEL 2 programmable parameters are setup to enable optimal tracking of the A4 signal. The auto-setup phase will occur while the MARVEL 2 features are in monitor mode (i.e. VDI pacing which is effectively VVI pacing). For purposes of evaluating the primary efficacy objective, the 20-minute resting period while the MARVEL 2 features are programmed to adaptive mode and providing VDD pacing will serve as each subject's treatment period.

Note that a randomized crossover design will *not* be used to compare AV synchronous pacing percentage between the MARVEL 2 pacing mode and VVI pacing for the following reasons: 1) knowledge of pacing mode is unlikely to influence AV synchronous pacing rate as such knowledge is unlikely to influence right atrial contractility, 2) the auto-setup phase will provide an opportunity to assess the AV synchronous pacing percentage during VVI pacing, 3) carryover effects are not possible since as soon as the MARVEL 2 features are programmed to adaptive mode atrial tracking will commence.

The accuracy spreadsheet derived from each Holter file (see section 7.5.2.3) will be used to determine the synchrony status (yes or no) for each P-wave. Each accuracy spreadsheet will be imported into SAS and/or R and the P-P interval computed for each P wave i (where $i > 1$) as the time in seconds in Column 1 (A) for the i^{th} P-wave minus the time in seconds in Column 1 (A) for the $i^{\text{th}}-1$ P-wave. Each P-wave in the accuracy spreadsheet file will be classified as being evaluable or not evaluable. P-waves that are not evaluable include:

1. P-waves with no ventricular sense or pace markers and indication of telemetry dropout in the first 300 ms after the P-wave. These are identified from the accuracy spreadsheet where column 13 (M) = 0 and column 14 (N) = 1.

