2. P-waves that occur during an AV conduction mode switch as these P-waves occur when the pacing mode is set temporarily to VDI40 while the device checks for intrinsic AV conduction. These are identified from the accuracy spreadsheet where a supplemental marker in the preceding P-P interval (column 15 (O) < P-P interval), and the pacing mode in the supplemental marker is VDI40, indicating a mode switch (column 17 (Q) = 7). Note that for the pacing mode, the supplemental marker indicates the pacing mode on the next ventricular event, which is why a look-back to the preceding supplemental marker is necessary to determine if the current ventricular event is in a mode-switched state.

All other P-waves in the accuracy spreadsheet will be considered evaluable. Evaluable P-waves will be considered synchronous if they occur within 300 ms of the following ventricular event. Thus, evaluable P-waves will be considered synchronous if column 2 (B) < 0.3 and asynchronous if column 2 (B) \geq 0.3.

For the analysis of the primary efficacy objective, P-waves with records in the accuracy spreadsheet corresponding to the auto setup phase (i.e. columns 11 (K) and 12 (L) indicate auto setup phase) or

resting phase (i.e. columns 11 (K) and 12 (L) indicate auto setup phase) will be selected. The auto setup phase will occur during MARVEL 2 monitor mode pacing (i.e. VVI pacing) and the resting phase will occur during MARVEL 2 adaptive mode pacing (i.e. VDD pacing). If at least 70% of evaluable beats are considered synchronous during the VVI or MARVEL 2 adaptive pacing mode during resting, then the subject will be considered to have met the primary efficacy endpoint during the VVI or MARVEL 2 adaptive pacing mode during rest respectively. McNemar's test for paired proportions will be used to test the primary efficacy objective hypothesis. Note that subjects with fewer than 500 evaluable beats during each period will be excluded from the primary efficacy analysis.

[REDACTED]

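### The protocol limits the efficacy endpoint to P-waves in normal sinus rhythm, but no readable rule for evaluable beats, in the protocol or the SAP, applies that limit

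*SAP*

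**What the plan says.** Protocol 8.2.1.1, in the rationale for the 300 ms definition, says that "only P-waves identified on surface ECG that occur during normal sinus node function will be considered for the endpoint", and that "P-waves occurring during atrial arrhythmias are not included in the endpoint definition". The reason given is that the algorithm should not, or could not, track such beats.

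The operational rules read differently:

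- **Protocol 17.5.3:** "An evaluable beat is defined as an observable P-wave on the Holter ECG followed by at least 300 ms" of dropout-free telemetry, or by a ventricular marker. There is no rhythm condition.
- **Protocol 17.5.5:** beats lost to telemetry dropout and beats during an AV conduction test are not evaluable. No other class is named.
- **SAP 7.5.3.4:** two non-evaluable classes, "P-waves with no ventricular sense or pace markers and indication of telemetry dropout in the first 300 ms after the P-wave" and "P-waves that occur during an AV conduction mode switch". Then: "All other P-waves in the accuracy spreadsheet will be considered evaluable".
- **SAP 7.5.3.6:** the same two classes.

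SAP 7.5.3.1 restates the 300 ms and 70% criteria without the sinus limit and refers to Protocol 8.2.1.1 for the rationale. Rhythm is otherwise used only per subject: Protocol 17.4 and SAP 7.1.5 classify the predominant rhythm from the auto-setup phase.

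**The concern.** The endpoint definition and the counting rule give different denominators whenever an atrial arrhythmia occurs during an analysed period. The subject-level screen does not close the gap. It looks at the auto-setup phase, which is the VVI control period, while the adaptive-mode result comes from the later resting period. Atrial arrhythmia is not an exclusion criterion in Protocol 11.4. A subject in sinus rhythm at setup who goes into an atrial arrhythmia at rest therefore stays in the analysis.

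Because screening uses the control period only, the extra P-waves would fall mainly in the adaptive period. They would lower the reported responder proportion in a study meant as pivotal evidence. Two rules that disagree also leave a choice that could be made after the Holter data are seen, by sponsor personnel who both review the recordings (Protocol 17.5.4) and run the analyses (Protocol 17.1).

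**Working it through.** **1. The plan's own power figure.** SAP 7.5.3.5 claims more than 90% power with n = 35, 50% discordant pairs, 90% of them favouring MARVEL 2, and two-sided alpha 0.05. Let the number of discordant pairs be d ~ Binomial(35, 0.5) and the favourable pairs given d be Binomial(d, 0.9), with rejection in favour of MARVEL 2. The exact McNemar test has power 94.8%, the uncorrected chi-square 96.9% and the continuity-corrected version 94.0%. The claim reproduces.

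**2. How much arrhythmia flips one subject.** From the documents: 20 minutes of rest and a 70% threshold. Assumed, because the documents do not give them: sinus synchrony s, sinus rate r per minute, atrial rate a per minute in arrhythmia, and q, the share of arrhythmic P-waves followed by a ventricular event within 300 ms. If ventricular events are unrelated to the P-waves, q ≈ 0.3 × ventricular rate / 60, so 60/min gives 0.30 and 100/min gives 0.50.

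Set [s·r·(20 − t) + q·a·t] / [r·(20 − t) + a·t] = 0.70 and solve for the minutes of arrhythmia:

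t = 20·(s − 0.70)·r / [(s − 0.70)·r + (0.70 − q)·a]

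| s | r | a | q | t (min) |
|---|---|---|---|---|
| 0.90 | 70 | 150 | 0 | 280/119 = 2.4 |
| 0.90 | 70 | 150 | 0.30 | 280/74 = 3.8 |
| 0.90 | 70 | 250 | 0 | 280/189 = 1.5 |
| 0.90 | 70 | 250 | 0.30 | 280/114 = 2.5 |
| 0.90 | 70 | 250 | 0.50 | 280/64 = 4.4 |
| 0.80 | 60 | 300 | 0 | 120/216 = 0.6 |
| 0.95 | 80 | 150 | 0.30 | 400/80 = 5.0 |
| 0.95 | 80 | 150 | 0.50 | 400/50 = 8.0 |

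Over s = 0.80–0.95, r = 60–80, a = 150–300 and q = 0–0.30, t runs from 0.6 to 5.0 minutes. Closer following (q = 0.50) lengthens it, to 8.0 minutes in the last row.

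**3. Two worked subjects, both with 90% sinus synchrony at 70/min.**

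- *Three minutes at 250/min, q = 0.30.* Sinus: 17 × 70 = 1,190 P-waves, 1,071 synchronous. Arrhythmia: 3 × 250 = 750, of which 225 synchronous. All P-waves: 1,296/1,940 = 66.8%, endpoint not met. Sinus only: 1,071/1,190 = 90.0%, endpoint met, and still above the 500-beat minimum.
- *Five minutes at 200/min.* Sinus: 15 × 70 = 1,050, of which 945 synchronous. Arrhythmia: 1,000 P-waves, with at most about one synchronous per ventricular event. At 60–80 ventricular beats/min that is 300–400, giving 1,245/2,050 = 60.7% to 1,345/2,050 = 65.6%, not met. At 100/min it is (945 + 500)/2,050 = 70.5%, met. Break-even is (0.70 × 2,050 − 945)/5 = 98/min.

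**4. Trial level, n = 35, exact test.** Suppose a share f of favourable discordant subjects become failures in both modes. The favourable cell is then 0.45·(1 − f) and the unfavourable cell stays at 0.05.

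| f | discordant share | favourable share of discordant | power |
|---|---|---|---|
| 0 | 0.500 | 0.900 | 94.8% |
| 5% | 0.4775 | 0.895 | 92.6% |
| 10% | 0.455 | 0.890 | 89.9% |
| 20% | 0.410 | 0.878 | 82.1% |

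At the prior-study rates (24 of 33 against 2 of 33) the documents give only the margins. The discordant cells could therefore be 22 and 0, 23 and 1, or 24 and 2. The lowest power over these, with f = 20%, is 99.0%.

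**The case against.** The strongest objection is the redaction. The SAP rule covers P-waves in the accuracy spreadsheet, and SAP 7.5.3.4 refers to its source: "The accuracy spreadsheet derived from each Holter file (see section 7.5.2.3"). All of SAP 7.5.2 is blacked out, and so are blocks in 7.5.3.4 and after the rhythm section. A reader might infer that every P-wave is counted and that the analysed responder status is certainly not the protocol's. The documents do not support that, because an upstream filter cannot be ruled out and redacted text is not missing text. What can be said is that the readable text shows no such filter. Protocol 17.5.4 says "A human overread will also be used to truth each P-wave" but names no rhythm flag. SAP 7.5.3.4 computes P-P intervals from adjacent rows, which suggests, without proving, that the rows are consecutive P-waves.

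Nor is this simply the SAP departing from the protocol. Protocol 17.5.3 and 17.5.5 omit the limit too, and SAP 7.5.3.1 does refer to the protocol section that contains it.

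A reader might also infer that any short arrhythmia makes a failure. It does not. An arrhythmia without visible P-waves adds nothing to the denominator, and one largely followed within 300 ms does not fail the subject. Protocol Table 4 puts typical tracking at up to around 100 bpm, and at that ventricular rate the five-minute example passes.

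Finally, the error works against the sponsor's own claim, and nothing in the documents suggests that 10–20% of responders would be affected. That limits the weight of the point but does not settle which rule applies.

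**Conclusion.** The inconsistency stands: the protocol's endpoint text carries a sinus-rhythm limit, and none of the four readable sections that define or apply evaluable beats does. Whether it changes any result depends on the redacted SAP 7.5.2.3 and on how often visible, untracked atrial arrhythmia occurs at rest, which the documents do not give.

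If there is no upstream filter, roughly 0.6 to 5 minutes of such arrhythmia would turn an otherwise successful subject into a failure, over the assumed rates with q up to 0.30. The bias is mainly against the device, since few subjects reach 70% in VVI (2 of 33 in the prior study). It lowers the responder proportion and the power, and does not inflate type I error. A loss of about 10% of favourable discordant subjects is needed to bring exact-test power just under 90% at the minimum planning assumptions. At prior-study rates the primary test result would probably not change. It is worth correcting because it decides which endpoint is reported and the correction is cheap, not because the trial's conclusion is in doubt.

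**What to change.** - Add a third non-evaluable class to SAP 7.5.3.4 and 7.5.3.6: *P-waves occurring during an atrial arrhythmia on surface ECG (CIP 8.2.1.1)*. If SAP 7.5.2.3 already removes them, cite that step instead.
- Keep the class to atrial arrhythmia. Anything broader, such as all beats outside normal sinus node function, could also drop sinus bradycardia and sinus tachycardia, which Protocol 17.4 groups under sinus node dysfunction. It would also give readers room to remove untracked beats.
- Identify the beats in the planned ECG overread by a pre-stated onset and offset criterion, without device markers, identically in the auto-setup and resting periods, and preferably without knowledge of the period.
- Align Protocol 17.5.3 and 17.5.5 with 8.2.1.1.
- Report the excluded P-waves per subject and period alongside the planned total and evaluable beat counts, and add a sensitivity analysis that keeps all P-waves.

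The cost is slightly fewer evaluable beats in a few subjects and a little more overread and analysis work.

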17.5.5 Determination of Subjects and Data for Analysis

All subjects with normal sinus node function and persistent 3rd degree AV block during Holter monitoring with at least 500 evaluable beats during VVI pacing and at least 500 evaluable beats during MARVEL 2 adaptive pacing in which the device is providing VDD pacing¹ will be included in the primary analysis for this objective. For *de novo* subjects, only data collected during the 20-minute resting period at pre-hospital discharge will contribute to the analysis of the primary objective. (Note that ancillary objective number five will compare the atrioventricular synchronous pacing rates observed at pre-hospital discharge and at 1-month post-implant.) However, if a *de novo* subject does not have usable Holter data at pre-hospital discharge, their Holter data approximately 1-month post-implant will be used in the analysis, if available.

¹ Cardiac cycles during MARVEL 2 adaptive mode pacing that occur during an AV conduction test will not be considered evaluable as the pacing mode is set temporarily to VVI40 while the device checks for intrinsic AV conduction.

Loss of communication between the Holter and the implanted Micra device, called telemetry dropout, can lead to loss of the marker indicating a ventricular event was sensed or a ventricular pace was delivered. Therefore, beats with no ventricular sense or pace markers and indication of telemetry dropout in the first 300 ms after a P-wave will be discarded (i.e. they are not evaluable beats).

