7.5.3.6 Determination of Subjects/Data for Analysis

All subjects with normal sinus node function and persistent 3rd degree AV block during Holter monitoring with at least 500 evaluable beats during VVI pacing and at least 500 evaluable beats during MARVEL 2 adaptive pacing in which the device is providing VDD pacing will be included in the primary analysis for this objective. For *de novo* subjects, only data collected during the 20-minute resting period at the pre-hospital discharge procedure will contribute to the analysis of the primary objective.

However, if a *de novo* subject does not have usable Holter data from the pre-hospital discharge procedure, their Holter data at the 1-month post-implant procedure will be used in the analysis, if available.

As described in section 7.5.3.4 cardiac cycles with no ventricular sense or pace markers and indication of telemetry dropout in the first 300 ms following a P-wave as well as P-waves that occur during an AV conduction check will be excluded from the primary analysis (i.e. they are not evaluable beats).

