7.5.3.7 Missing Data and Sensitivity Analyses

Missing Data

Given the relatively short duration of the study, missing data is not expected to be a serious issue. Since telemetry dropout may influence the number of evaluable beats for a subject during both VVI pacing

and MARVEL 2 adaptive pacing, the total number of heart beats and total number of evaluable beats will be summarized.

Missing Data Sensitivity Analyses

If any subjects with normal sinus node function and persistent 3rd degree AV block do not have usable Holter data during the study, the reason the Holter data was not usable will be discussed. Additionally, to address concerns with missing data that may arise, sensitivity analyses will be performed to assess the robustness of the observed statistical inference with respect to the missing data.

The first sensitivity analysis will be to include all subjects with normal sinus node function and persistent 3rd degree AV block that had some usable Holter data during both 20-minute resting period (MARVEL 2 adaptive pacing) and VVI pacing control period (i.e. auto-setup phase) regardless of the number of evaluable beats in each phase.

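### SAP 7.5.3.4 selects the resting phase with the auto-setup code, and its dropout rule ties beat inclusion to marker survival, with a bias whose direction the readable text leaves open

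*SAP*

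**What the plan says.** **Phase selection.** SAP 7.5.3.4 takes the P-waves for the primary efficacy analysis from two phases, identified by spreadsheet columns 11 (K) and 12 (L). The auto-setup phase is selected where those columns indicate auto-setup. The second phase is given as "resting phase (i.e. columns 11 (K) and 12 (L) indicate auto setup phase) will be selected". The next sentence then separates the two: auto-setup is monitor mode, and "the resting phase will occur during MARVEL 2 adaptive mode pacing (i.e. VDD pacing").

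**Dropout.** The same section makes not evaluable "P-waves with no ventricular sense or pace markers and indication of telemetry dropout in the first 300 ms after the P-wave", coded as "column 13 (M) = 0 and column 14 (N) = 1". Apart from beats during a conduction check, every other P-wave is evaluable. It is synchronous if the next ventricular event comes in under 0.3 s. Protocol 17.5.5 carries the same rule ("beats with no ventricular sense or pace markers and indication of telemetry dropout in the first 300 ms after a P-wave will be discarded"). Protocol 17.5.3 defines an evaluable beat as an observable P-wave "followed by at least 300 ms of drop-out free Holter telemetry data or a Micra ventricular event marker".

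**Safeguards.** SAP 7.5.3.6 requires "at least 500 evaluable beats during VVI pacing and at least 500 evaluable beats during MARVEL 2 adaptive pacing". In SAP 7.5.3.7, "the total number of heart beats and total number of evaluable beats will be summarized", and the first sensitivity analysis removes the 500-beat floor.

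**The concern.** The first matter is a programming rule for the primary endpoint that is wrong as printed. It names the control period twice and the treatment period never.

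The second is selection at beat level. Whether a dropout P-wave stays in the denominator depends on whether a ventricular marker was received, and the timing of that marker is also what decides synchrony. Inclusion is therefore not independent of outcome. Each subject's percentage is cut at 70%, so a shift of a few points can change the status of a subject close to the threshold. One subject in 35 is 2.9 percentage points of a responder rate (1/35). The readable sensitivity analyses deal with subjects who have few beats or missing recordings, or with repeat visits. None varies the beat-level rule. Total and evaluable counts do not show how many dropout beats were kept because of a marker.

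**Working it through.** **1. The plan's own figure.** SAP 7.5.3.5 claims over 90% power with 35 subjects, 50% discordant pairs, 90% of them favouring MARVEL 2 and two-sided alpha 0.05. Enumerating discordant pairs as Bin(35, 0.5) and favourable pairs as Bin(k, 0.9) gives 94.8% for exact McNemar, 96.9% for the uncorrected asymptotic test and 94.0% with continuity correction. The claim reproduces.

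**2. The selector taken literally.** No resting rows are returned, so no subject can reach 500 adaptive-mode beats. If the auto-setup rows were used in both roles, every pair would be concordant and power would be 0. With the correct code, the figures in step 1 stand.

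**3. The dropout rule.** The documents give no dropout or marker-survival rates, so these inputs are assumed:
- d = share of P-waves with dropout in the first 300 ms, taken as unrelated to synchrony
- r = share of synchronous dropout beats whose marker is still received
- s = true synchrony

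*Reading A: column M covers only the first 300 ms.* A dropout beat is kept only if it is synchronous.

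Observed = s(1 − d + dr) / [s(1 − d + dr) + (1 − s)(1 − d)]

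True synchrony that scores 70% = 0.7(1 − d) / (1 − d + 0.3dr):

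| d | r = 0 | r = 0.5 | r = 1 |
|---|---|---|---|
| 10% | 70.0% | 68.9% | 67.7% |
| 20% | 70.0% | 67.5% | 65.1% |
| 30% | 70.0% | 65.8% | 62.0% |

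Example that changes status: 1,000 P-waves, s = 68%, d = 20%, r = 0.5. The 800 clean beats hold 544 synchronous. Of 136 synchronous dropout beats 68 are kept; of 64 asynchronous ones none are. Score = (544 + 68)/(800 + 68) = 612/868 = 70.5%, so a non-responder becomes a responder.

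*Reading B: column M covers any marker in the cycle.* Asynchronous dropout beats with a later marker are kept (here, all of them). A synchronous beat that lost its marker is either dropped or, if a later marker is picked up, scored asynchronous. With q = 1 − d + dr, the true synchrony that scores 70% is 0.7/(0.7 + 0.3q) if dropped and 0.7/q if scored asynchronous. At d = 20% and r = 0.5, q = 0.9, giving 0.7/0.97 = 72.2% and 0.7/0.9 = 77.8%.

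Example: 1,000 P-waves, s = 75%, same d and r. There are 600 synchronous clean beats and 75 synchronous dropout beats with a marker. If the other 75 are scored asynchronous, the score is 675/1,000 = 67.5%, so a responder becomes a non-responder. If they are dropped, it is 675/925 = 73.0%.

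**4. Excluding every dropout beat.** The same two subjects score 544/800 = 68.0% and 600/800 = 75.0%, their true values, under either reading.

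**5. Effect on the test.** At the prior study's VVI mean of 37.5%, Reading A at its extreme (d = 30%, r = 1) gives 0.375/(0.375 + 0.625 × 0.7) = 46.2%, still far below 70%. Prior-study responders were 24 of 33 in adaptive mode and 2 of 33 in VVI, so discordant counts lie between 22 vs 0 and 24 vs 2. From 22 vs 0, losing 17 favourable subjects leaves 5 vs 0, exact p = 0.0625. From 24 vs 2, losing 15 leaves 9 vs 2, p = 0.065. The uncorrected asymptotic test needs 16 to 19 losses.

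**The case against.** **On the selector.** The sentence itself names the resting phase, the next one assigns it to adaptive mode, and SAP 7.5.3.4 earlier makes the 20-minute rest the treatment period. A literal run would return an empty set and be noticed at once. The spreadsheet description (SAP 7.5.2.3) is redacted and may give the right codes. This stands as far as consequences go. A reader might infer that the primary analysis would be run on the wrong rows; the documents do not support that. What remains is that the readable rule is wrong and nothing readable corrects it.

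**On dropout.** A marker received within 300 ms proves synchrony, so discarding it throws away known data. Dropout is acknowledged, beat counts are reported and there is a beat floor. This is a sound reason to keep the primary rule. It does not remove the selection, because the rule's treatment of the remaining dropout beats still depends on marker survival.

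A reader might go further and infer that the rule inflates synchrony and so flatters the device. The text does not establish that. Protocol 17.5.3 sets no time limit on the marker, and SAP 7.5.3.6 states the exclusion in terms of cardiac cycles, which fits Reading B as well. The direction turns on a redacted definition, and redaction is not a fault of the plan. Nor can the absence of further beat-level reporting be proved, since text following the primary analysis is also redacted.

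**Conclusion.** Minor, in two parts.

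The selector error is certain. It is a copy error in an operative primary-endpoint rule, with the intent clear.

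The dropout rule makes inclusion depend on marker survival; that follows from the text. Its direction is not settled. On Reading A measured synchrony rises whenever some markers survive, and the rule is neutral if none do. On Reading B it falls to the extent that late markers survive dropout more often than early ones. At an assumed 20% dropout and half of markers surviving, the true value that scores 70% is 67.5% on Reading A and 72.2% to 77.8% on Reading B. Only subjects near the threshold can change status. A subject whose true synchrony is exactly 70% already meets the endpoint, so inflation changes nothing for that subject.

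A reader might infer that the superiority result is at risk. With prior-study counts, 15 or more favourable subjects would have to be lost first, so the McNemar conclusion is unlikely to change. What could move is the reported responder percentage.

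**What to change.** 1. In SAP 7.5.3.4, change the second selector so that columns 11 (K) and 12 (L) indicate the resting phase. This is one phrase.
2. State the time window that column 13 (M) covers, or cross-refer to it if SAP 7.5.2.3 already gives it.
3. Keep the primary dropout rule. In SAP 7.5.3.7, prespecify a sensitivity analysis that treats every P-wave with column 14 (N) = 1 as not evaluable in both phases, whatever column 13 (M) shows. Report by phase the dropout beats excluded and those retained because of a marker.

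Item 3 removes the dependence on marker survival under either reading, provided dropout is unrelated to synchrony.

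The cost is one extra run on data already held, with no protocol revision. Replacing the primary rule instead would mean revising protocol 17.5.3 and 17.5.5 and discarding beats of known synchrony, which is not warranted. The sensitivity run has fewer evaluable beats. At an assumed 60 bpm for 20 minutes (1,200 P-waves), 20% dropout leaves 960 and 30% leaves 840. A subject falls below 500 only above 1 − 500/1,200 = 58% dropout.
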